11.1 Potential Risks to Subjects

Risk of Fluid Administration: Patients in the liberal fluid protocol may receive additional intravenous fluids. This carries the potential risk of fluid overload, including acute congestive heart failure, breathing difficulties, and increased peripheral edema.

Risk of Vasopressor Administration: Patients in the restrictive protocol may receive early or additional vasopressors based on the treatment assignment. The potential risks of early vasopressors include cardiac ischemia, cardiac dysrhythmias, bowel ischemia, or limb ischemia.

Risks of Blood Draws: All patients will have blood drawn for research purposes. Many patients will have invasive lines placed for clinical purposes, where the risk of blood draws are extremely low, as blood can usually be easily obtained from these lines. In cases where an invasive line is not present, the risks of drawing blood are uncommon and include bleeding and bruising. Commonly, drawing blood is painful, and rarely, drawing blood can lead to infections at the site of the blood draw.

Risk of Line Placement: Patients with hypotension will often have central venous access placed to increase venous access in the anticipation of the need for reliable and increased access for fluid, medication, and vasopressor administration. However, if restoration of blood pressure occurs without needing vasopressor medications, clinicians may decide to not place central venous access. Additionally, clinicians may opt to use peripheral venous access to administer vasopressors. The restrictive fluids protocol is intended to facilitate an increase in the utilization of vasopressors; thus, this practice may lead to an increase in the placement of central venous catheters. The decision to place a central venous line will be left to the treating and/or study clinician. It is possible that additional central venous catheters will be placed in the fluid restrictive group. The risks of central venous access include infection, pneumothorax (punctured lung), and vessel injury, inclusive of inadvertent arterial cannulation.

Peripheral Vasopressor Utilization: Peripheral vasopressor administration is permitted in this protocol. The risk of peripheral vasopressors utilization is extravasation and soft-tissue toxicity/injury if extravasation occurs.

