- Cardiovascular events: need for vasoactive drugs or fluids for hypotension or hypotension, Supraventricular/ventricular tachycardia (SVT) or new onset atrial fibrillation (AF). The occurrence of one or more episodes (sustained for more than 1 minute for SVT and AF) during the hospital stay will be recorded.
- Respiratory events: decreased PaO₂/FiO₂, hypoxia, worsening acute respiratory distress syndrome, or respiratory failure.
- Hepatic events: hepatic injury or liver dysfunction that leads to an increase from baseline in the serum level of bilirubin.
- Renal events: renal failure, renal insufficiency, or renal injury that leads to an increase from baseline in serum creatinine.
- Hematologic/coagulation events: coagulopathy, disseminated intravascular coagulation, thrombocytopenia, or thrombocytosis.

Note: Arrhythmias such as heart block or ventricular fibrillation are not considered study specific clinical outcomes and should be recorded as adverse events if they are serious events or are considered by the investigator to be related to study procedures.

G4. Decision tree for determining if an adverse event is reportable

Adapted from Ranieri VM, Thompson BT, Barie PS et al. Drotrecogin alfa (activated) in adults with septic shock. *N Engl J Med.* 2012 May 31;366 (22):2055-64. Epub 2012 May 22. PubMed PMID: 226168

H. Imputed P/F using SpO2 and FiO2

The equivalence table below determines the estimated P/F ratio from the FiO2 and SpO2. This data was generated by investigators at the University of Utah, on a cohort of critically ill patients with pneumonia [32-38].

SPO2	FiO2														
	0.3	0.35	0.4	0.45	0.5	0.55	0.6	0.65	0.7	0.75	0.8	0.85	0.9	0.95	1
80%	148	127	111	98	89	81	74	68	63	59	55	52	49	47	44
81%	151	129	113	101	91	82	76	70	65	60	57	53	50	48	45
82%	155	132	116	103	93	84	77	71	66	62	58	55	52	49	46
83%	158	136	119	106	95	86	79	73	68	63	59	56	53	50	47
84%	162	139	122	108	97	89	81	75	70	65	61	57	54	51	49
85%	167	143	125	111	100	91	83	77	71	67	63	59	56	53	50
86%	171	147	129	114	103	94	86	79	73	69	64	61	57	54	51
87%	177	151	132	118	106	96	88	81	76	71	66	62	59	56	53
88%	182	156	137	121	109	99	91	84	78	73	68	64	61	58	55
89%	189	162	141	126	113	103	94	87	81	75	71	67	63	60	57
90%	196	168	147	130	117	107	98	90	84	78	73	69	65	62	59
91%	203	174	153	136	122	111	102	94	87	81	76	72	68	64	61
92%	213	182	159	142	128	116	106	98	91	85	80	75	71	67	64
93%	223	191	168	149	134	122	112	103	96	89	84	79	74	71	67

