### Adverse Events

Adverse events will be analyzed using weighted Poisson regression with non-serious events weighted by one and serious events weighted by two. Events rather than patients will be the unit of analysis. Adverse events will be grouped and analyzed separately by MedDRA system organ classes.

The analysis is intention to treat and significance testing will be two-tailed at  $\alpha = 0.05$  with no adjustment made for multiple comparisons.

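### Adverse events are compared only by organ class, so heart failure and cardiac ischemia may partly offset and ischemia is never compared as one harm

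*SAP*

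**What the plan says.** SAP section 5, Adverse Events, sets the model: "Adverse events will be analyzed using weighted Poisson regression with non-serious events weighted by one and serious events weighted by two". It continues: "Events rather than patients will be the unit of analysis", and then: "Adverse events will be grouped and analyzed separately by MedDRA system organ classes". Tests are two-tailed at 0.05 "with no adjustment made for multiple comparisons". The section plans no comparison by individual term or by type of harm.

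Protocol 11.1 describes the expected harms by treatment. For fluids: "This carries the potential risk of fluid overload, including acute congestive heart failure, breathing difficulties, and increased peripheral edema". For the restrictive arm: "The potential risks of early vasopressors include cardiac ischemia, cardiac dysrhythmias, bowel ischemia, or limb ischemia". It adds, for infusion through a peripheral line: "The risk of peripheral vasopressors utilization is extravasation and soft-tissue toxicity/injury if extravasation occurs".

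Several of these harms are covered outside the adverse event analysis. SAP 1.9 has arrhythmia to day 28 (item 13), early ventricular arrhythmia (14c), respiratory endpoints (14a, 14b, 14e, 14m), line complications (14i to 14k) and extravasation (14l). Nothing in that list covers cardiac, bowel or limb ischemia, or acute heart failure.

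Protocol Appendix G3 largely exempts study outcomes from adverse event reporting, including supraventricular and ventricular tachycardia, new atrial fibrillation and respiratory events. It keeps some rhythm events in, provided that they are serious or judged related: "Arrhythmias such as heart block or ventricular fibrillation are not considered study specific clinical outcomes and should be recorded as adverse events". Ischemia and heart failure are not among the exempt examples.

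**The concern.** The protocol predicts opposite harms in the two arms. Grouping by organ works against that prediction in two ways.

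- **Offset.** Acute heart failure (expected excess in the liberal arm) and cardiac ischemia (expected excess in the restrictive arm) would probably be counted in one cardiac class. Each excess then reduces the difference made by the other.
- **Splitting.** Cardiac, bowel and limb ischemia share a mechanism but would probably be coded to different classes. Each test would see only part of the signal, mixed with unrelated events. Protocol 5.1 and 5.2 place suspected bowel and limb ischemia under a single criterion for leaving study guidance, so the protocol already treats them together. The SAP does not.

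Because these two harms have no endpoint of their own, the class tests are the only planned comparison of ischemia and of heart failure as a diagnosis. A flat cardiac class could be read as reassurance about both.

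**Working it through.** **Per-arm size.** The documents give no adverse event rate and no power for adverse events. The only stated figure that can be checked is the sample size (Protocol 9.1): 15% vs 10.5%, two-sided alpha 0.05, power 0.90, total 2320.

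n per arm = [1.960·√(2·0.1275·0.8725) + 1.282·√(0.15·0.85 + 0.105·0.895)]² / 0.045² = 1153, or 2306 in total. This agrees with 2320 for a fixed design. At 1160 per arm the power is 0.902.

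**Test used.** Event counts X and Y are independent Poisson with equal exposure. The test rejects when |X − Y| / √(X + Y) > 1.96. Power is summed exactly over the two distributions. Counts are unweighted. Rates are assumed, and expected count = 1160 × rate.

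**Offset.** Let heart failure have rate a in the liberal arm and b in the restrictive arm.
- Full offset: cardiac ischemia is b vs a, so the class is (a + b) vs (a + b).
- Half offset: the ischemia excess is half as large, so the class is (a + b) vs (b + (a + b)/2). For a = 3% and b = 1%, that is 46.4 vs 34.8 expected events.

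| Heart failure, liberal vs restrictive | Tested alone | Class, full offset | Class, half offset |
|---|---|---|---|
| 1% vs 0.5% | 0.29 | 0.05 | 0.08 |
| 2% vs 1% | 0.51 | 0.05 | 0.11 |
| 3% vs 1.5% | 0.68 | 0.05 | 0.15 |
| 3% vs 1% | 0.94 | 0.05 | 0.25 |

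**Splitting.** Total ischemia is spread evenly over three classes. The last two columns add 2% unrelated events per arm to each class. The chance that at least one class rejects is 1 − (1 − p)³, assuming independence and no adjustment.

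| Ischemia, restrictive vs liberal | Combined | Each class | Any of three | Each class, 2% background | Any of three, 2% background |
|---|---|---|---|---|---|
| 2% vs 1% | 0.51 | 0.19 | 0.46 | 0.08 | 0.22 |
| 3% vs 1% | 0.94 | 0.51 | 0.88 | 0.16 | 0.42 |

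Without background events, looking for any of three rejections comes close to the combined test. But three unadjusted tests at 0.05 carry a false-positive chance of up to 1 − 0.95³ = 0.14. The clear loss comes when unrelated events share the classes, as they would in patients this ill.

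**The case against.** A reader might infer that every harm named in Protocol 11.1 is tested only within organ classes. The documents do not support that. Dysrhythmia, respiratory consequences, line complications and extravasation have their own endpoints, and the SAP tests categorical secondary outcomes by Chi-square or Fisher's exact test. Signs of fluid overload are collected during the protocol phase (Protocol 7.2) and appear to fall under the SAP's On Study Variables analysis. That rule does not name heart failure.

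The cardiac offset is also narrower than it looks. Most tachyarrhythmias stay out of the adverse event data, so it is mainly heart failure against cardiac ischemia, plus heart block and ventricular fibrillation.

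Three limits on the numbers stand:
- Power of 0.05 needs exact balance. With heart failure 20 vs 8 and cardiac ischemia 2 vs 6 (liberal vs restrictive), the class is 22 vs 14 and power is about 0.27.
- The SAP's test weights serious events by two. The powers above are for unweighted counts and are not those of the SAP's test.
- The documents do not give the MedDRA hierarchy. Which events share a class is inferred from the term for the grouping.

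Finally, the DSMB reviews adverse events (Protocol Appendix G), and organ-class testing does not prevent tables by term. So it would be too strong to say that these harms would go undetected. What remains is that no planned comparison isolates heart failure or brings ischemia together.

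**Conclusion.** The point holds in a limited form. For acute heart failure and for cardiac, bowel and limb ischemia, the SAP's only planned comparison is by organ class. That grouping probably sets the first against part of the second and divides the rest. It does not show that the cardiac comparison must be null, or that the trial leaves its named harms unexamined.

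Across the assumed rates, the cardiac class has power of 0.05 to 0.25 where separate tests would have 0.29 to 0.94. Each ischemia class has 0.19 to 0.51 where a combined group would have 0.51 to 0.94. The direction of the loss follows from the grouping, given the inferred mapping and the opposite effects that the protocol expects. Its size rests on rates that the documents do not give, on how far the cardiac excesses balance, on an even spread of ischemia, and on unweighted counts. This is an inexpensive improvement to the safety analysis and does not touch the primary outcome.

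**What to change.** Add to the SAP's Adverse Events section two pre-specified groups that cut across organ classes:

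1. Acute heart failure or fluid overload.
2. Cardiac, bowel or limb ischemia.

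Leave dysrhythmia and extravasation out of the second group. SAP 1.9 already covers them, and including them would dilute the ischemia comparison. Because treatment is open-label, fix the list of coded terms for each group before anyone preparing the analysis sees adverse events by arm. Compare each group as patients with at least one event among all randomized patients, with a risk difference and 95% confidence interval. Keep the organ-class analysis alongside.

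The cost is a paragraph, a short term list and two more safety comparisons, with no new data. One limit should be stated in the report: the overload count may be incomplete, because respiratory events are largely exempt from adverse event reporting and Protocol 13.1 itself says that hydrostatic and other pulmonary edema are hard to tell apart.

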### On Study Variables

The analysis of pre-specified and systematically collected on study variables will be similar to that of the secondary outcomes. Variables that are measured daily will be compared between treatment groups on each study day with no adjustment made for multiple comparisons.

The analysis is intention to treat and significance testing will be two-tailed at  $\alpha = 0.05$ .

### Secondary Analysis by Subgroups

The secondary analysis of the primary and secondary outcomes by subgroups will use the same methods as the primary except that the statistical models will be augmented with subgroup and subgroup by treatment interaction terms.

The analysis is intention to treat and significance testing will be two-tailed at  $\alpha = 0.05$  with no adjustment made for multiple comparisons.

### Missing Data

Analysis is based on all available data with no imputation of missing data; except in the case of selected derived variables, for example SOFA variables.-

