**11. 90-day all-cause mortality**

We will contact patients at day 90 to ascertain their survival status. This will be done by telephone contact with the patient or family members as well as a review of medical records and publicly available data sources. We will use the national death index as a final check for patient with whom we are unable to confirm their vital status through other means.

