#### 5. Statistical Methods

##### Primary Outcome

The primary outcome is intention-to-treat 90-day all cause in-hospital mortality, where in-hospital includes both study and discharge hospitals (i.e. transfer hospitals or LTAC). Subjects who are discharged home (defined as residence prior to admission) prior to day 90 will be assumed to be alive at day 90. Analysis of the primary outcome will be based on the Kaplan Meier day 90 mortality point estimates with all patients who are discharged home or still alive at day 90 censored at day 91, which is beyond the last possible day of death. The day 90 mortality estimates in the two treatment groups will be compared by a Z-test using Greenwood's standard error (Kalbfleisch, J. D. and Prentice, R. L. (1980), *The Statistical Analysis of Failure Time Data*, New York: John Wiley & Sons.).

If there is no loss to follow up then the primary outcome will be compared between treatment groups on the risk difference scale using a generalized linear model with a binomial distribution function and identity link function.

The hypothesis regarding the primary outcome is a two-sided superiority hypothesis.

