### Secondary Outcomes

Continuous secondary outcomes will be compared between treatment groups using a t-test.

Categorical secondary outcomes will be compared between treatment groups using a Chi-square or Fisher's exact test as appropriate to the sparseness of the data.

The analysis is intention to treat and significance testing will be two-tailed at  $\alpha = 0.05$  with no adjustment made for multiple comparisons.

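### 90-day all-cause mortality is tested on available data with no rule for patients whose day-90 status stays unresolved, while the less exposed primary mortality outcome gets Kaplan-Meier

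*SAP*

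**What the plan says.** Outcome 11 is defined in SAP 2.2 and, in the same terms, in Protocol 3.6.2. Ascertainment is active: "We will contact patients at day 90 to ascertain their survival status". The sources are "telephone contact with the patient or family members as well as a review of medical records and publicly available data sources", and then a last step: "We will use the national death index as a final check for patient with whom we are unable to confirm their vital status". Neither document says whether a patient searched in the index without a match counts as alive, is censored, or is missing.

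No test is named for outcome 11 itself. It is a yes/no outcome, so the general rule in SAP section 5 (Secondary Outcomes) applies: "Categorical secondary outcomes will be compared between treatment groups using a Chi-square" or Fisher's exact test. The Missing Data paragraph adds "Analysis is based on all available data with no imputation of missing data", with an exception only for selected derived variables such as SOFA.

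The primary outcome is handled differently: "Analysis of the primary outcome will be based on the Kaplan Meier day 90 mortality point estimates", compared by a Z-test with Greenwood's standard error. A binomial model replaces this only under a condition: "If there is no loss to follow up then the primary outcome will be compared between treatment groups on the risk difference scale". The primary outcome also carries a rule that removes most post-discharge loss: "Subjects who are discharged home (defined as residence prior to admission) prior to day 90 will be assumed to be alive at day 90".

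**The concern.** The two mortality endpoints are treated in the wrong order of need. For the primary outcome, a patient who goes home is settled by definition. For outcome 11, that same patient has to be traced to day 90. The endpoint that depends on tracing has the method that cannot use partial follow-up, and the endpoint that hardly depends on it has the method that can. The switch to a binomial model only when nobody is lost shows that the SAP anticipated some loss.

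Observed survival is also wasted. Protocol 12.5 keeps data recorded up to withdrawal in the analysis unless consent to use them is withdrawn too. Protocol Appendix F schedules vital status at day 28 as well as day 90. A patient known alive at day 28 and unresolved at day 90 contributes nothing to a Chi-square on day-90 status.

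Outcome 11 matters because it counts the deaths after discharge home that the primary definition sets aside. Readers will use it as the check on the primary result.

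**Working it through.** **The plan's own figure.** The documents give no loss rate and no design figure for outcome 11. The only related figure is the primary sample size of 2,320 (15% against 10.5%, two-sided 0.05, 90% power). The fixed-sample formula is n = [1.96·√(2·0.1275·0.8725) + 1.2816·√(0.15·0.85 + 0.105·0.895)]² / 0.045². It gives 1,153 per arm, or 2,306 in total, which agrees with 2,320. This confirms the arm size used below (1,160) but does not bear on the concern itself.

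**Inputs for the bias check (all assumed).** 15% of patients die in a facility (exponential times, mean 12 days). 80% go home (mean about 9 days), and 5% of all patients die after going home, evenly up to day 90. The other 5% remain in a facility, alive. True mortality is therefore 20%. A share L of home-discharged patients is lost at discharge, at random, and no later search recovers any of them.

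**Complete case.** Mortality = (0.15 + 0.05·(1 − L)) / (1 − 0.80·L). For L = 5% this is 0.1975 / 0.96 = 20.57%, too high by 0.57 points.

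**Kaplan-Meier.** Lost patients are censored at discharge; the values come from a simulation of 4 million patients.

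| L | Complete case | Excess (points) | Kaplan-Meier excess (points) |
|---|---|---|---|
| 1% | 20.11% | 0.11 | 0.06 |
| 3% | 20.34% | 0.34 | 0.19 |
| 5% | 20.57% | 0.57 | 0.32 |
| 8% | 20.94% | 0.94 | 0.53 |
| 10% | 21.20% | 1.20 | 0.67 |

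Kaplan-Meier removes a little under half of the excess. Some remains because home patients carry lower risk (5/80 = 6.25% post-discharge mortality) than the patients still at risk when they are censored.

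**Effect on the comparison, unequal loss.** With 3% lost in one arm and 8% in the other, the false difference is 20.94 − 20.34 = 0.60 points for complete case and about 0.35 for Kaplan-Meier. The standard error of the difference is √(2·0.20·0.80/1,160) = 1.66 points.

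**Effect on the comparison, equal loss.** Take true rates of 15% and 10.5%, and let u be the share of survivors unresolved in both arms. Complete-case mortality is m / [m + (1 − m)(1 − u)]. The difference moves from 4.50 to 4.53 points at u = 1%, 4.67 at 5% and 4.86 at 10%.

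**Direction.** Suppose 5% of all patients are unresolved, true mortality is 15%, and a share q of the unresolved died. Complete-case mortality is (0.15 − 0.05q)/0.95. This is 15.8% at q = 0, 15.0% at q = 15% and 14.2% at q = 30%. The overstatement therefore requires the unresolved to be at lower risk than average.

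**The case against.** A reader might infer that the SAP drops these patients and so overstates mortality. The documents do not support that as a statement of fact. The death index is aimed at exactly the patients in question, and the SAP does not classify a non-match. If a non-match counts as alive and nobody else is unresolved, there is no bias. Nor is the direction fixed: nothing in the documents says unresolved patients are mostly low-risk survivors, and early withdrawals need not be. This objection stands, and the conclusion has to be conditional.

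The size can also be challenged fairly. Every loss rate is assumed. The model lets no later search recover anyone, and it ignores the day-28 check. Equal loss barely moves the risk difference. The unequal-loss case needs contact at day 90 to depend on the arm of a 24-hour intervention. The trial is unblinded, but no passage makes that link. Even then the false difference is well inside one standard error. All of this stands and keeps the point minor.

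It would also be too strong to present Kaplan-Meier as a cure: on these inputs it leaves more than half of the excess.

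The objection does not remove the inconsistency itself. Patients who withdraw or cannot be searched remain possible, and a Chi-square on day-90 status cannot use their follow-up.

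**Conclusion.** The concern holds in a limited form. As written, outcome 11 is analysed by a test that cannot use patients unresolved after the ascertainment chain, while the less exposed primary outcome has a method that can.

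If unresolved patients are excluded and are at lower risk than average, mortality is overstated in each arm. Under the stated assumptions and 1% to 10% loss, the excess is about 0.1 to 1.2 points with complete-case analysis and 0.06 to 0.7 with Kaplan-Meier. The between-arm contrast is distorted mainly when loss differs by arm: about 0.6 against 0.35 points at 3% versus 8%, with a standard error of about 1.7. The effect approaches zero as the death index resolves more patients. This is an improvement worth making, not a threat to the trial's conclusions.

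**What to change.** In SAP section 5, Secondary Outcomes, take outcome 11 out of the Chi-square rule and add:

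- Day-90 all-cause mortality is compared by Kaplan-Meier estimates with Greenwood's standard error and a Z-test, using date of death or date last known alive. The day-91 censoring rule for patients discharged home does not apply.
- A patient searched in the national death index without a match is counted alive through the date the search covers. A patient who cannot be searched is censored when last known alive.
- The number of patients unresolved at day 90 is reported by arm.

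An estimator that treats being at home as a separate state could address the remaining bias. It is a different analysis from the Z-test above and was not checked here, so at most it belongs as an optional sensitivity analysis.

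Cost: a few sentences in the SAP, plus recording the date of death or last known alive after discharge home. The primary analysis does not need those dates, because it stops following patients once they return home. With complete follow-up, the Kaplan-Meier estimate equals the simple proportion, so nothing is lost.
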